D2.3. Sleep extension intervention. After completing baseline testing, subjects will be randomized, stratified by sex, to either: 1) *sleep extension* for 4-6 wk (n=25) or 2) *continued habitual short sleep* for 4-6 wk followed by 4-6 wk *sleep extension* (n=25). Randomization will be accomplished using the online randomization module of REDCap, a secure, web-based application designed to support data capture for research studies¹⁰⁰. Permuted blocks with varying block sizes will be used to ensure that there is no temporal bias in group assignment. When randomization occurs, the study coordinator will enter the REDCap system and will be asked to respond to a series of questions establishing the eligibility of the subject. The randomization assignment will only be revealed if all eligibility criteria are satisfied. We chose a 6-wk sleep extension intervention, because the only published study that showed a potential benefit of sleep extension on metabolic function used a 6-wk sleep extension protocol⁴⁸. Sleep and circadian expert members of the research team will use the baseline assessments to develop an individualized targeted intervention for each subject randomized to the sleep extension group with the goal of increasing each subject's sleep schedule by ~2h/night to reach a minimum of 7h/night. We chose 7.0h/night as a cut-off for short sleepers, since it is the minimum recommendation from the American Academy of Sleep Medicine recommendation for our targeted age-range (i.e., 18-65 years old). Our preliminary data on sleep extension in this age-group demonstrate our ability to extend sleep by over 2h/night (Table 1, section **C2.5**).

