Actiwatch weekly, and provide participants weekly feedback about maintaining a consistent schedule. When daily call-ins are reviewed, subjects will be sent a text message letting them know to keep on track or remind them to maintain their extended sleep schedule if they report deviations from the planned schedule (i.e. bedtime ± 30 min from scheduled bed time and/or wake-time ± 15 min away from scheduled wake-time). In our preliminary data extending sleep in this age group, 14 of 15 subjects were able to extend sleep. If participants report 3 consecutive unscheduled deviations of ± 30 min for bedtime or ± 15 min for waketime they will be asked to come to the laboratory and their sleep schedule will be verified by downloading the Actiwatch data. If participants are unable to adhere to the sleep extension protocol they will be withdrawn from the study. Lastly, a urinary toxicology screen will be performed at week 2 to ensure subjects continue to abstain from recreational drug use.

D2.4. Repeat testing. After subjects complete 4-6 wk of sleep extension or habitual sleep, all visits and procedures performed during baseline testing will be repeated. In addition, the DXA scan and questionnaires completed at screening will be repeated. Subjects will continue their assigned sleep duration until all follow-up tests are completed. Subjects randomized to the *continued habitual short sleep* group will have the opportunity to receive a personalized sleep treatment plan provided by our Sleep Medicine Center after the study is completed.

D2.5. Sample analyses and calculations

Blood samples. All blood sample analyses are routinely performed in our laboratories. Blood samples for inflammatory markers (C-reactive protein, IL-6, TNF α and MCP-1 concentrations) and estrogen and progesterone concentrations will be measured by using high sensitivity ELISA kits. Plasma C-peptide and insulin concentrations will be measured by using an Elecsys assay. Plasma melatonin will be analysed by Buhmann RIA. Total, reduced and oxidized glutathione will be assessed in plasma by using a commercially available colorimetric assay (Cayman Chemicals, Ann Arbor, MI). Plasma FFA will be quantified by using gas chromatography¹¹⁰. Plasma glucose and palmitate TTRs will be determined by using gas chromatography-mass spectroscopy^{86,110}.

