D4.1. Data analyses. Statistical evaluation of the study data will be conducted in collaboration with [name], a biostatistician in the Washington University Institute of Clinical and Translational Sciences (ICTS) Research Design & Biostatistics Group. We will use a modified intention-to-treat (mITT) analysis, in which all subjects that complete the study will be analyzed regardless of their adherence to the assigned sleep intervention (i.e., continued short sleeping pattern in the control group and successful sleep extension [adding ~2 h of time-in-bed per night ensuring at least 7h/night] in the sleep extension group). Analysis of covariance (ANCOVA) with the post-treatment value as the dependent variable will be used to determine whether there are between group differences in our metabolic outcomes assessed during the HEC procedure and 24-h blood sampling study with the pre-intervention value used as a covariate. Characteristics at baseline between groups will be compared by using t-tests or Wilcoxon's test for continuous variables and chi square tests for dichotomous variables; any significant differences between groups will be used to adjust subsequent statistical analyses when necessary. Violations of the assumption of homogeneity of variance and/or sphericity will be corrected, if necessary, via transformation of data to produce data that satisfy normality and equal variance assumptions^{90,121-123}. As this protocol incorporates a 2-time point, pre-post study design there is no basis to input follow-up data when only baseline data are available. Because of this limitation, we will compare characteristics between completers and non-completers by using t-tests or Wilcoxon's test for continuous variables and chi square tests for dichotomous variables; these results will be reported in addition to the ANCOVA analysis. Metabolite analyses will be performed by using an ANOVA and Tukey post-hoc testing for statistical significance between conditions and across time. For discovery based untargeted metabolomics analysis, a conservative statistical threshold will be applied at the outset (Bonferroni corrected P value of $<10^{-5}$ to account for multiple hypothesis testing). To further minimize false discovery, we will also use principal component analysis as well as sparse partial least squares and LASSO regression with internal cross-validation. Metabolites identified using these methods will be prioritized for future investigation as potential mechanisms underlying sleep related metabolic improvements.

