D7.4 Ambitious project that requires highly committed subjects, considerable organizational efforts, and interpretation of complex datasets. We have an experienced participant recruitment core with access to a large pool of potential participants, a strong track record in recruiting subjects who meet specific

requirements, excellent participant compliance and retention in studies as rigorous or more rigorous than the current proposal, extensive experience in performing the complex metabolic studies proposed in this application, and expertise in conducting all sample analyses and interpretation of data needed for this project e.g.,^{21,31,36,67,74-88,90,92,94,108,110,129,130}. [name] will serve as the biostatistician for this project and, will ensure appropriate statistical procedures and adjustments for potential confounding variables and drop-outs are used.

D7.5 Effect of study participant age on sleep architecture. The age of our study participants will range from 18-65 years old. We chose this range to increase our ability to identify people with MUO, which is much less common in younger age groups. This age range has implications for sleep, because there is a marked reduction in slow wave sleep (considered to be the most physically restorative sleep stage) and a reduction in sleep efficiency that begins in early adulthood^{131,132}. Accordingly, people who are 18-65 years old are likely to have room for improvements in sleep. However, as noted in section **D1** and **D2.2**, participants who have insomnia or other clinically significant sleep disorders will be excluded and participants who are unable or unwilling to extend sleep will be removed from the study.

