D7.6 Menstrual cycle in women. Women who are menstruating will be selected on the basis of a history of regular menstrual cycle ranging in length from 25-32 days with a maximum of 3 days variation month-to-month. We will use plasma progesterone and estrogen levels from the HEC procedure days and use menstrual phase as a co-variate in our analyses. To account for menstrual phase, we will initiate the pre- and post-intervention studies in the early follicular phase (confirmed by plasma progesterone and estrogen). Women with Late Luteal Phase Dysphoric Disorder will be excluded from participation because of alterations in sleep and circadian function associated with mood disorders. Postmenopausal women will also be included in this study to increase our ability to identify subjects with prediabetes or hyperinsulinemia. Since postmenopausal women could have lower sleep quality when not using hormone replacement therapy¹³³, participants who have clinically significant sleep disorders will be excluded.

D7.7 Clinical relevance. This study will determine whether sleep extension in people with MUO who are short-sleepers has therapeutic effects on a series of key metabolic and inflammatory outcomes that are associated with sleep restriction. Accordingly, this study will prove or disprove this specific question, but is not meant to establish whether sleep extension is possible in a real world setting or what specific approaches are needed to extend sleep in clinical practice.

E. PROTECTION OF HUMAN SUBJECTS

E1. Risks to the subjects

E1.1. Human Subjects Involvement and Characteristics. A total of 50 human subjects, aged 18-65 years old, will be studied. Subjects will be carefully screened with a medical history and physical examination, blood tests, an oral glucose tolerance test and resting electrocardiogram (see section **D1.** for details of inclusion/exclusion criteria). Mentally disabled persons, prisoners, pregnant and lactating women, and persons whose ability to grant voluntary informed consent is questionable will not be recruited.

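### Minor: the primary ANCOVA fixes only the baseline value as a covariate, leaves all others to baseline significance tests, and omits sex, the randomisation stratum

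*Combined protocol and SAP*

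**What the plan says.** D4.1 specifies ANCOVA of the post-treatment value for the clamp and 24h outcomes, "with the pre-intervention value used as a covariate". It then has baseline characteristics compared between arms by t, Wilcoxon or chi-square tests, and adds: "any significant differences between groups will be used to adjust subsequent statistical analyses when necessary". It does not list the characteristics, give a threshold for those tests, say when adjustment is needed, or say whether the adjusted or the unadjusted result is primary.

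Three other sections bear on the model:

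- **D2.3:** "subjects will be randomized, stratified by sex, to either" arm. D5 says the arms will be balanced on sex, but no section makes sex a model term.
- **D7.4:** the biostatistician will see that "adjustments for potential confounding variables and drop-outs are used". No variables are named.
- **D7.6:** the team will "use menstrual phase as a co-variate in our analyses". It also says "we will initiate the pre- and post-intervention studies in the early follicular phase". D4.1 does not mention menstrual phase.

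D4.1 analyses only those who complete the study. D2.3 says "If participants are unable to adhere to the sleep extension protocol they will be withdrawn from the study", and D7.5 says "participants who are unable or unwilling to extend sleep will be removed from the study".

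**The concern.** Two analysts could follow D4.1 faithfully and fit different primary models to the same data. The baseline p-value is also a poor way to choose covariates. Under correct randomisation a significant difference is a chance event, and its p-value says nothing about whether the variable predicts glucose Rd.

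The rule will almost never bring sex in, because stratification balances it. Yet stratifying on a prognostic factor and then leaving it out of the model makes the reported standard error too large. At stake are a uniquely defined primary estimate, a p-value that means what it says, and a little precision.

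**Working it through.** **1. The plan's own figure.** D4.2.1 gives a difference of 7.9 and an SD of 6.4 µmol/kg FFM/min, so d = 7.9/6.4 = 1.23. A two-sample t-test (noncentral t, two-sided 5%) has 90.4% power with 15 per arm and 88.2% with 14, so the stated 15 per arm reproduces. With the 25 per arm planned in D2.3, power is 99.0%. No covariate enters this calculation.

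**2. Omitting sex: type I error.** Let sex explain a share s of the residual variance after baseline adjustment. The documents give no value; s = 10% and 20% are assumed. With sex balanced by design, the effect estimate has variance (1 − s) × 2σ²/n, but the model without sex reports about 2σ²/n. A nominal 5% test then rejects only when |t| exceeds the critical value divided by √(1 − s).

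- 25 per arm, 47 df, critical value 2.012.
- s = 10%: 2.012/√0.9 = 2.121, giving 3.9%.
- s = 20%: 2.012/√0.8 = 2.249, giving 2.9%.

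Simulation agrees: 4.0% and 3.0% (50 participants, half women, assumed permuted blocks of 2, 4 and 6 within sex, 20,000 replicates).

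**3. Omitting sex: power.** Same simulation, residual SD including sex set to 1.

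| Setting | s | Sex omitted | Sex included | Loss (points) |
|---|---|---|---|---|
| 25/arm, 1.23 SD | 10% | 98.95% | 99.22% | 0.3 |
| 25/arm, 1.23 SD | 20% | 99.34% | 99.70% | 0.4 |
| 10% loss, 1.23 SD | 10% | 98.18% | 98.60% | 0.4 |
| 10% loss, 1.23 SD | 20% | 98.64% | 99.42% | 0.8 |
| 15/arm, 1.23 SD | 10% | 89.9% | 91.8% | 1.8 |
| 15/arm, 1.23 SD | 20% | 91.3% | 94.7% | 3.4 |

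Losses are from unrounded values. If instead 6.4 is the SD within each sex and sex adds a difference of one SD on top, the losses are 98.8 − 97.6 = 1.2 points at 25 per arm and 89.4 − 83.9 = 5.5 at 15 per arm. A chi-square test flags sex among completers in at most 0.05% of simulated trials, so the D4.1 rule does not repair the omission. If sex explains nothing, including it costs at most 0.4 points.

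**4. The significance rule.** The number of candidate variables (5, 8 or 20) and their joint strength (30% of residual variance) are assumed; 25 per arm, 40,000 replicates.

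- Chance that at least one independent test is significant: 1 − 0.95^5 = 23%, 1 − 0.95^8 = 34%, 1 − 0.95^20 = 64%. This is how often the rule triggers, not the harm it does.
- Rule applied mechanically: type I error 3.8 to 4.5%.
- Smaller p-value of the models with and without the flagged variables: 5.4, 5.8 and 6.0% (independent candidates); 5.5, 5.9 and 7.6% (pairwise correlation 0.3).
- Best p-value over any subset of flagged variables: up to 6.8% (independent) and 7.9% (20 correlated candidates).

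A separate simulation with 5 to 15 independent candidates explaining 20 to 50% gives 3.6 to 4.7% for mechanical use and 5.3 to 6.1% for the smaller of two p-values.

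**5. Withdrawal from the extension arm.** The only extension non-compliance figure in the documents is 1 of 15 (D2.3, D7.3), and 25 × 1/15 = 1.7, so about 2 of 25. In the worst case one baseline variable alone decides who leaves. Removing the 2 lowest of 25 then shifts that arm's mean by about 0.15 SD. If the variable correlates 0.3 to 0.5 with the outcome after baseline adjustment (assumed), the bias without it in the model is 0.15 × 0.3 = 0.045 to 0.15 × 0.5 = 0.075 SD, or 0.3 to 0.5 µmol/kg FFM/min at SD 6.4. Under the D4.1 rule it is about 0.03 to 0.05 SD, and with the variable always in the model about 0.

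**The case against.** The strongest reply has four parts.

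- **The outcome's baseline value is fixed, and there is an implied order.** D4.1 tests baseline characteristics and then adjusts later analyses, so choosing a model with results in view is a worst-case reading. This stands as far as it goes: not every covariate is open, and nothing in the documents says the choice will be made on results. But an implied order is not a list or a dated decision, and the primary result remains undefined.
- **Sex hardly matters.** The 6.4 is day-to-day variability, to which a stable trait should contribute little, and the baseline value absorbs much of any stable sex difference. This stands. It makes the 10 to 20% share generous and the power argument weak. It gives no reason to leave out a stratum that costs almost nothing to include.
- **Menstrual phase is largely handled by design**, because testing starts in the early follicular phase with hormonal confirmation. This stands. What is open is whether phase enters the primary model and how it is coded for men and postmenopausal women.
- **Withdrawal bias argues against simply deleting the rule.** The rule removes some of that bias, and a model with only arm, baseline and sex removes none of it. This stands, and it shapes the fix.

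A reader might infer that withdrawal makes the covariate rule seriously harmful. The documents do not support that. Losing 5 of 25 would be well above 1 of 15, D1 screens for ability to extend sleep before randomisation, and D4.1 reports completers against non-completers (which discloses selection without removing it). The bias comes from analysing completers only; the rule does not create it.

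**Conclusion.** The point holds as a minor one. The primary model is incompletely specified and leaves out the stratum.

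Omitting sex makes the test conservative, with type I error of about 4% or 3% at an assumed 10% or 20% of residual variance. The power loss at the planned effect is under 1 point with 25 per arm when 6.4 is taken to include sex, and about 2 to 4 points at 15 per arm, which is the plan's power basis and not its planned size.

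A reader might infer that the significance rule inflates the false-positive rate substantially. It does not: mechanical use gives about 4%, results-driven choice about 5.5 to 6% with independent candidates, and about 8% only with 20 correlated candidates and selection of the best result. Candidate number, covariate strength and the sex share are all assumptions. That the text does not define the primary model needs none of them.

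**What to change.** In D4.1, state the primary model for the clamp and 24h outcomes as post value = arm + baseline value of that outcome + sex, and delete the rule that adjusts for significant baseline differences.

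If the team expects a baseline variable to predict both glucose Rd and withdrawal from the extension arm, name it now and put it in the primary model. A sensitivity analysis alone is not enough, because the bias from analysing completers stays in any model that omits the variable. Label every other adjusted model as a sensitivity analysis, and align D7.4 with this.

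Reconcile D7.6 with D4.1: say whether menstrual phase belongs to the primary model or to a sensitivity analysis, and define its coding for men and postmenopausal women. A not-applicable category would overlap with sex.

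The cost is one degree of freedom for sex (at most about 0.4 points of power if sex explains nothing), one more for each single-term covariate named, and no new data. The change must be dated. The documents do not say whether outcomes have been seen by arm, and section F has study data reviewed yearly with the investigators present. If outcomes by arm have been seen, disclose that the change came afterwards.

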D2.2.1. Inpatient CRU Visit 1 (24h metabolic profile, and assessment of PSG, circadian misalignment, oxidative stress and systemic inflammation). Participants will be admitted at ~1800h and stay in the CRU for ~36h and will continue their usual ≤ 7.0 h/night sleep schedule.

24h blood sampling and urine collection. Approximately 30 min after awaking on Day 2, after subjects fast for ~11.5h overnight, a catheter will be inserted into an antecubital vein. This catheter will be connected to a 12-ft long, small-lumen extension tubing that will be passed through a wall portal to allow blood sampling without disturbing the participant. Blood samples will be obtained hourly for 24h starting 1h after awaking (i.e., immediately prior to breakfast) to assess glucose, FFA, C-peptide, insulin, and melatonin concentrations [a total of 25 blood samples (3 mL each)]. Blood samples obtained every 3h will be used to assess: i) markers of inflammation (C-reactive protein, IL-6, TNF α , MCP-1, and selected prostanoids [prostaglandin PG E_2 , PGD $_2$ PGF $_{2\alpha}$ and thromboxane A $_2$]); ii) markers of oxidative stress (plasma oxysterols and glutathione-to-oxidized glutathione ratio), and markers of insulin resistance (branched-chain amino acids, aromatic amino acids, glycine, and glutamine, and acetylcarnitine C2)⁹³. An additional 10 mL of blood will be obtained every 3h to isolate PBMCs, which will be used to evaluate the expression of clock genes. PBMCs will be immediately isolated through a density gradient centrifugation by using the Histopaque-1077 (#10771; Sigma, St. Louis, MO). Subjects will be seated for at least 15 min before each blood sample because posture can impact melatonin levels⁹⁴. Light exposure during 24h sampling will be <8 lux max (~1.9 lux angle of gaze), because bright light suppresses melatonin, our primary marker of circadian phase^{90,95}. At other times during the study subjects will be exposed to normal room lighting (e.g., 200 lux). Meals will be supervised to ensure all food is consumed within 30 min. Urine will be collected throughout the 24h blood sampling protocol to determine urinary 8-iso-prostane F2 α content as a marker of oxidative stress.

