Metabolomics. State-of-the-art mass spectrometry techniques will be used to measure specific circulating metabolites that have been linked with metabolic dysfunction and/or sleep restriction, including markers of inflammation, oxidative stress, and insulin resistance (see section **D2.2.1**). These metabolites will be evaluated in blood samples obtained every 6h for 24h to provide an integrated assessment of plasma concentrations throughout the day. Additionally, we will measure a key marker of oxidative stress in a 24h urine collection (urinary 8-iso-prostane F2 α)^{62,63}. To capture these metabolites of interest, multiple complementary LC methods will be performed as previously described^{62,63}, each optimized to capture a chemical subset of the metabolome, and coupled to a high resolution Thermo Orbitrap QExactive mass spectrometer. This orthogonal chromatography will include hydrophilic interaction liquid chromatography (HILIC) using a Sequent Zic-pHILIC HPLC column to capture polar metabolites, reverse phase chromatography using a superficially porous Phenomenex Kinetex C18 UPLC column to capture lipids and peptides, and weak ion exchange chromatography using a Phenomenex Luna aminopropyl HPLC column to capture sugars, nucleotides, and phosphates. Metabolites of interest are definitively identified by using MS/MS analysis, with matching of LC measures and MS/MS fingerprint to commercial metabolite standards. In addition to targeted measures, simultaneous untargeted metabolomics analyses will be performed to comprehensively identify novel metabolites that may be associated with sleep related improvement in metabolic function. These metabolite markers will serve as the basis for future investigation and potentially enable discovery of novel metabolite biomarkers and bioactives involved in improved metabolic function induced by sleep extension in persons with MUO.

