Molecular analyses. Total RNA will be isolated from PBMC, muscle and adipose tissue biopsy samples in Trizol reagent (Invitrogen, Carlsbad, CA) or RNeasy kit (Qiagen, Valencia, CA). Real time-PCR will be used to determine gene expression^{36,67,87,88}. Expression of clock genes (e.g. *CLOCK*, *BMAL1*, *PER1*, *PER2*, *CRY1*, *CRY2*, *REV-ERBa*, *DBP*) in PBMC and markers of inflammation (e.g. *IL6*, *TNF*, *CCL2*, *CD68*) and oxidative stress (e.g. *NQO1*, *DHCR24*, *UCHL1*)³⁶ in muscle and adipose tissue will be determined. Adipose tissue protein carbonylation will be evaluated with an OxyBlot Protein Oxidation Detection Kit (Millipore)¹¹¹.

Circadian Melatonin Phase Assessment. Blood samples from the 24h blood sampling studies will be used to measure melatonin concentrations to determine the Dim Light Melatonin Onset (DLMO) and the Dim Light Melatonin Offset (DLMOFF) (linear interpolation of 25% of the fitted peak to trough amplitude), as we have

done previously^{108,112-114}. We will also calculate the timing of the midpoint between the DLMO and DLMOFF. We considered other circadian phase markers (e.g. core body temperature and cortisol), but will use melatonin because it is the most precise and accurate marker of circadian phase in people¹¹⁵.

Calculation of substrate and hormone kinetics. Endogenous glucose and palmitate Ra into the circulation and glucose Rd will be calculated as we have previously described^{36,87}. The hepatic insulin sensitivity index will be calculated as the reciprocal of the product of endogenous glucose Ra and basal plasma insulin concentration¹¹⁶. The adipose tissue insulin resistance index will be calculated as the product of endogenous palmitate Ra and basal plasma insulin concentration¹¹⁷. Plasma substrate and hormone concentration areas-under-the-curve for 5 h after initiating meal consumption and for the entire 24h will be calculated by using the trapezoid method¹¹⁸. Insulin secretion will be estimated by C-peptide deconvolution during the 24h blood sampling study¹¹⁹ and insulin clearance rates by dividing the ISR AUC by the insulin AUC over each meal period and over the full 24h and by compartmental modelling during the HEC procedure¹²⁰.

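### Transforming the data does not in general correct a sphericity violation, and the serial metabolite ANOVA has no other safeguard

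*Combined protocol and SAP*

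**What the plan says.** All the relevant analysis wording is in D4.1.

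- **Assumption violations.** "Violations of the assumption of homogeneity of variance and/or sphericity will be corrected, if necessary, via transformation of data". The sentence ends with what the transformation is to achieve: "via transformation of data to produce data that satisfy normality and equal variance assumptions". No epsilon correction, multivariate test or mixed model is named.
- **Clamp and 24h-sampling outcomes.** "Analysis of covariance (ANCOVA) with the post-treatment value as the dependent variable", covering the clamp and the "24-h blood sampling study with the pre-intervention value used as a covariate". In D2.5 the 24h curves are reduced to areas, which "for the entire 24h will be calculated by using the trapezoid method".
- **Metabolites.** "Metabolite analyses will be performed by using an ANOVA and Tukey post-hoc testing for statistical significance between conditions and across time". D2.5 gives the sampling: "These metabolites will be evaluated in blood samples obtained every 6h for 24h". Aim 1, hypothesis iv, gives the same six-hourly interval.

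The plan does not say what time means in the metabolite ANOVA, or whether it is a within-subject factor.

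**The concern.** Sphericity requires that the differences between every pair of repeated measurements have the same variance. It therefore depends on covariances as well as variances. A transformation works on one measurement at a time. It can even out the variances, but it has no direct handle on the pattern by which nearby samples agree more than distant ones. The two targets that D4.1 names, normality and equal variance, do not together amount to sphericity.

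Sphericity can fail only with three or more within-subject levels. In a pre-post trial analysed by ANCOVA the rule has nothing to act on except serial samples within a visit, and the metabolite ANOVA is the one analysis specified across time. If that ANOVA is run as a standard repeated-measures analysis with transformation as the only safeguard, its time and group-by-time tests can be too liberal. Tukey comparisons that use the pooled within-subject error share the faulty assumption. The claims at stake are those under Aim 1, hypothesis iv, that sleep extension alters particular plasma metabolites.

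**Working it through.** **Inputs.** From the documents: 25 participants per arm (D2.3) and metabolite samples every 6h for 24h (Section A, D2.5). That is five points per visit if both ends are kept, or four if one is dropped. D4.2 sets a two-sided 5% level for its listed outcomes; I take the same level for the targeted metabolites, for which none is stated. Assumed, because the documents give no correlations: first-order autoregressive (AR(1)) correlation with adjacent-sample correlation ρ from 0.3 to 0.9. The plan states no error rate for any repeated-measures test, so there is no figure of its own to reproduce.

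**Step 1: departure from sphericity.** With S the covariance matrix of the k samples and D its double-centred form, ε = [tr(D)]² / [(k − 1) Σ dᵢⱼ²]. Sphericity is ε = 1.

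**Step 2: type I error of the group-by-time test, k = 5.** Data were simulated with no true effect, already normal and with equal variances, so the stated aim of the transformation is fully met (20,000 trials per row). The uncorrected F test has 4 and 48 × 4 = 192 degrees of freedom.

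| Correlation | ε | Uncorrected | Greenhouse-Geisser |
|---|---|---|---|
| Compound symmetry, 0.5 | 1.000 | 4.6% | 4.2% |
| AR(1), 0.3 | 0.919 | 5.8% | 5.0% |
| AR(1), 0.5 | 0.809 | 6.0% | 4.6% |
| AR(1), 0.7 | 0.689 | 7.1% | 4.7% |
| AR(1), 0.9 | 0.577 | 8.4% | 5.1% |

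A repeat simulation put the low end at 5.4%. The Box approximation agrees. The uncorrected critical value is 2.42, and P(F with 4ε and 192ε df > 2.42) is 5.5% at ε = 0.919 and 8.6% at ε = 0.577. With four points the uncorrected error is 5.2-7.1%. With 15 per arm and five points it is 5.0-8.2%, and 3.9-5.0% after Greenhouse-Geisser. The between-group test, with participant modelled, stays at 4.8-5.2% across the rows of the table.

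**Step 3: does transformation help?** Lognormal data with a diurnal pattern, five points, correlation 0.7, 25 per arm:

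| Log-scale correlation | Raw | After log | After log, Greenhouse-Geisser |
|---|---|---|---|
| Compound symmetry (violation due only to variance rising with the mean) | 6.8% | 5.0% | 4.5% |
| AR(1) | 6.7% | 7.2% | 4.7% |

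The log transformation cures the violation in the first case and not in the second.

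**Step 4: time as an ordinary factor with independent errors.** The between-group F statistic is then inflated by about λ = 1 + (2/k) Σ (k − d)ρᵈ, summed over d = 1 to k − 1, and the error rate is about P(|Z| > 1.96/√λ).

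- ρ = 0.3: λ = 1 + 0.4 × (1.2 + 0.27 + 0.054 + 0.0081) = 1.61; 1.96/√1.61 = 1.54; error 12%.
- ρ = 0.9: λ = 1 + 0.4 × (3.6 + 2.43 + 1.458 + 0.6561) = 4.26; 1.96/√4.26 = 0.95; error 34%.

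**The case against.** **The main results are untouched.** This stands. A reader might infer that the 24h-sampling results in general are at risk. They are not: glucose Rd and the 24h glucose and insulin AUCs enter the ANCOVA as one value per participant, where sphericity does not arise.

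**Longer series.** A reader might extend the point to the hourly series, where 25 points would give larger inflation. No such repeated-measures test is planned. Nine points are only an inference. D2.2.1 says "Blood samples obtained every 3h will be used to assess" inflammatory, oxidative-stress and insulin-resistance markers, but nothing puts those nine samples into the ANOVA as repeated measures.

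**Time may mean before and after.** D4.1 describes a pre-post design with two time points, and D2.5 presents the six-hourly samples as giving an overall picture of the day. If each visit is reduced to one value, time has two levels and sphericity holds automatically. The reading is fair and cannot be excluded. But the plan specifies no such summary for metabolites, and on that reading the sphericity rule would have nothing to govern. It makes the inflation conditional; it does not make the rule correct.

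**Transformation is not useless.** This stands. Step 3 shows it working when unequal variance is the only cause.

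**The randomised contrast is safe.** It is if participant is modelled, which the plan does not say. Step 4 shows what follows otherwise.

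**Untargeted metabolomics uses a much stricter threshold.** This stands, so the 5% figures here apply to the targeted metabolites only.

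**Greenhouse-Geisser does not repair Tukey tests.** This stands. It adjusts the F test and leaves pooled-error comparisons as they were. The size of the Tukey problem was not simulated.

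**Conclusion.** The point holds in a limited form. D4.1 names a remedy that does not in general address the assumption it is meant to address, and the one analysis planned across time has no other protection. If time of day is the within-subject factor, the uncorrected group-by-time test at five points has about 5.4-8.4% error instead of 5%. If the repeated samples are treated as independent, the between-group test has about 12-34%.

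These sizes rest on the assumed AR(1) pattern, on 25 participants per arm and on a 5% level. The documents do not support saying that the error will exceed 5%: under compound symmetry it does not, and under the pre-post reading the question does not arise. The effect is moderate and confined to the targeted serial metabolites. It is still worth correcting, because the stated rule is wrong and the better one is readily available.

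**What to change.** Replace the sentence on assumption violations in D4.1, and the metabolite ANOVA sentence, with wording such as:

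> Transformation will be used for skew or unequal variance. Serial metabolite outcomes will be analysed with a mixed model (participant as random effect, baseline-visit value as covariate, group, time of day and group-by-time interaction, with a covariance that allows serial correlation). Multiplicity-adjusted comparisons will be taken from that model. If repeated-measures ANOVA is used instead, degrees of freedom will be Greenhouse-Geisser corrected, and post-hoc comparisons will use contrast-specific rather than pooled error terms.

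If the intention is one summary value per visit, say so, define the summary, and analyse it by the same ANCOVA as the AUCs; no sphericity rule is then needed. Make the change before the metabolite data are analysed.

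The cost is a little more analysis work and somewhat less liberal P values. Participants, sampling and sample size do not change.
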